8 ADVERSE EVENT/EXPERIENCE MONITORING

8.1 Definition

An **Adverse Event/Experience** is any unexpected or undesirable experience occurring to a subject during a study, which may or may not be related to the test device. All adverse events will be recorded and reported according to the Standard Operating Procedures of Princeton Consumer Research.

Events should be considered AEs if they:

- result in discontinuation from the study,
- require treatment or any other therapeutic intervention,
- require further diagnostic evaluation (excluding a repetition of the same procedure to confirm the abnormality),
- are associated with clinical signs or symptoms judged by the Investigator to have a significant clinical impact.

An Adverse Event is not:

- A surgical procedure
- A situation where an untoward event did not occur, (e.g. a social hospitalization)
- Baseline conditions that have not worsened in severity or frequency

Skin irritation is expected and graded at Visits 3 – 23 and will not be reported as an adverse event unless it leads to withdrawal from the study.

A **Serious Adverse Event/Experience** is any adverse experience occurring that results in any of the following outcomes:

- * death;
- * a life-threatening adverse experience;
- * inpatient hospitalization or prolongation of existing hospitalization;
- * a persistent or significant disability/incapacity;
- * a congenital anomaly/birth defect

Important medical event/experiences that may not result in death, be life-threatening, or require hospitalization may be considered a serious adverse experience when, based upon appropriate medical judgment, they may jeopardize the patient or subject and may require medical or surgical intervention to prevent one of the outcomes listed in this definition.

An **Unexpected Adverse Event/Experience** is any adverse event/experience not listed in the current labeling for the test device.

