8.2 Follow-up

Investigators should follow AEs until the event has resolved, the condition has stabilized, is well characterized, or referred for appropriate medical management, whichever comes first. Events and follow-up information occurring after the last visit should be recorded in the source documentation. Investigators are not obliged to solicit adverse events after a subject's final visit, however, if an investigator learns of an SAE that is believed to be possibly related to the study products, an SAE report form should be submitted.

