8.3 Notification

The Sponsor will be notified of all adverse event/experiences. Any Serious or Unexpected Adverse Event/Experience which occurs during the study must be reported promptly by the Investigator to the Sponsor and the reviewing IRB, as applicable, within 24 hours of the information being reported to Princeton Consumer Research.

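### Section 8.1 keeps graded skin irritation off the adverse event list unless it causes withdrawal, which conflicts with three of its own four AE criteria and leaves the status of challenge reactions at the last visit unclear

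*Combined protocol and SAP*

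**What the plan says.** Section 8.1 (Definition) gives four grounds on which an event should be considered an AE. The first is discontinuation from the study. The others are events that "require treatment or any other therapeutic intervention", events that call for further diagnostic work-up, and events that "are associated with clinical signs or symptoms judged by the Investigator to have a significant clinical impact".

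Later in the same section comes the rule for the graded endpoint: "Skin irritation is expected and graded at Visits 3 – 23", and it "will not be reported as an adverse event unless it leads to withdrawal from the study".

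Two duties then depend on AE status. Section 8.2 says "Investigators should follow AEs until the event has resolved, the condition has stabilized, is well characterized, or referred for appropriate medical management". That duty can run past the end of the schedule, since "Events and follow-up information occurring after the last visit should be recorded in the source documentation". Section 8.3 says "The Sponsor will be notified of all adverse event/experiences", with a 24-hour limit for serious or unexpected events.

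Under Safety Assessments, the Synopsis names AE monitoring as the means of assessing safety. Section 1.3 makes it the secondary objective.

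**The concern.** The study applies nine induction patches, allows a rest, and then challenges naive skin to see whether sensitization has occurred. The skin event that matters most for a subject's safety is therefore a challenge reaction. It is graded on the same Skin Irritation Scale as everything else, at visits that fall inside the range named in the exclusion.

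An investigator facing such a reaction finds two instructions in 8.1 that point in different directions. If the irritation sentence is followed, the reaction stays off the AE list even when it needs treatment. The obligations to follow it and to notify the sponsor formally then fall away. Two investigators could classify the same reaction differently, and the AE table that serves the secondary objective would reflect that choice.

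**Working it through.** The protocol has no calculation on this point. The check compares the rules with each other and with the schedule.

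**Timing of the last reading (Table 5-1, 5.5 to 5.7).** The challenge patch goes on at Visit 11 (Day 36) and comes off at Visit 12 (Day 38). Readings follow at Visits 13, 14 and 15 (Days 39, 40 and 41).

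- Last reading after patch removal: 41 − 38 = 3 days.
- Last reading after application: 41 − 36 = 5 days.
- Visits scheduled after Visit 15: none. The withdrawal exception can hardly apply there.

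**Status of a challenge reaction at Visit 15 under each part of 8.1.**

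| Feature of the reaction | Criteria list | Irritation sentence, read literally | Agreement |
|---|---|---|---|
| Leads to discontinuation | AE | AE | Yes, but can hardly arise at Visit 15 |
| Needs treatment | AE | Not an AE | Conflict |
| Needs further diagnostic evaluation | AE | Not an AE | Conflict |
| Significant clinical impact | AE | Not an AE | Conflict |
| None of these | Not required to be an AE | Not an AE | Yes |

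The two parts conflict on 3 of 4 criteria, and no sentence in 8.1 ranks one above the other.

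**What follows from AE status.** Sections 8.2 and 8.3 both apply to AEs. In the three conflicting rows, the list leads to follow-up and notification, while the literal irritation sentence leads to neither. Sections 5.7, 6.6 and 6.8 require scores, a narrative, photographs where applicable and the Investigator's opinion on sensitization. None of them requires a further look after Visit 15.

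**Visit range.** Sections 5.2, 5.3, 5.6 and 5.7 place skin evaluations at Visits 2-10 (9 visits) and 12-15 (4 visits): 9 + 4 = 13. The range in 8.1 runs from 3 to 23, which is 23 − 3 + 1 = 21 visit numbers:

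- graded visits: 3-10 (8) + 12-15 (4) = 12;
- Visit 11, with no skin evaluation: 1;
- Visits 16-23, which do not exist in a 15-visit study: 8;
- total: 12 + 1 + 8 = 21.

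Visit 2 is graded but left out. The range as printed and the corrected range both contain Visits 12-15, so the numbering error neither creates the conflict nor removes it.

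**The case against.** The strongest reply is that 8.1 states a general rule followed by a specific exception, and that the exception is narrow. It concerns irritation that is expected. Section 6.8 treats irritant reactions and sensitization as different findings. On that reading suspected sensitization was never excluded, and a reaction needing treatment is an AE that 8.2 follows past the last visit. Not listing the graded outcome a second time as an AE is a deliberate and common-sense choice. AE recording also follows the site's procedures, which may settle the matter and which are not among the documents.

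Much of this stands. The narrow reading is reasonable, and under it what remains uncovered is a reaction that needs no treatment or work-up and is judged not clinically significant. But the narrow reading is not written down, and the sentence as worded admits one exception only, withdrawal.

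A reader might infer more than the documents support:

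- *That challenge reactions are hidden from the sponsor.* They are not. All skin responses are reported, photographs of reactions of concern are shared with the sponsor, and the narrative and the Investigator's opinion are documented (6.6, 6.8). What may be lost is AE listing, formal notice under 8.3 and follow-up under 8.2.
- *That any reaction still visible at Visit 15 needs a compulsory recheck.* Nothing in the documents shows harm from leaving an untreated, clinically insignificant reaction unchecked.
- *That the sensitization result is compromised.* The rules in 6.8 use the scheduled induction and challenge scores and do not depend on AE status.

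**Conclusion.** The point holds as an internal conflict in 8.1, together with silence on suspected sensitization. Its practical effect is confined mainly to the end of the schedule. It bears on AE listing, follow-up and notification, and not on the primary assessment.

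The conclusion assumes that the irritation sentence may be read literally and that the site's procedures do not already resolve the conflict. If either assumption fails, what is left is a request for clarity. With other reporting routes open and a reasonable narrower reading available, the severity is minor.

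**What to change.** In 8.1, add one sentence: the exclusion of graded irritation does not apply to suspected sensitization at challenge, or to any skin reaction that meets one of the listed AE criteria. Section 8.2 then applies as it stands, and such a reaction is followed after Visit 15 until one of its existing endpoints is met. In the same place, change the visit range to Visits 2-10 and 12-15. That is a numbering correction only.

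A separate score-based recheck trigger is not needed. If the sponsor wants one, it should rest on suspected sensitization or Investigator concern. The excessive-irritation rule in 6.6 was written for moving induction patches and fits this purpose poorly: it would call a subject back for a single papule at grade 0, yet its letter grades omit weeping and induration.

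The cost is a sentence and a corrected range. Reacting subjects may need a few extra follow-up contacts. If 1 to 3 are assumed, that is 1/15 = 6.7% to 3/15 = 20% on top of the 15 visits for that subject, and none for others. A suspected sensitization will appear both in the AE list and in the sensitization result, so the final report needs a cross-reference between them.

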8.2 Follow-up

Investigators should follow AEs until the event has resolved, the condition has stabilized, is well characterized, or referred for appropriate medical management, whichever comes first. Events and follow-up information occurring after the last visit should be recorded in the source documentation. Investigators are not obliged to solicit adverse events after a subject's final visit, however, if an investigator learns of an SAE that is believed to be possibly related to the study products, an SAE report form should be submitted.

8.3 Notification

The Sponsor will be notified of all adverse event/experiences. Any Serious or Unexpected Adverse Event/Experience which occurs during the study must be reported promptly by the Investigator to the Sponsor and the reviewing IRB, as applicable, within 24 hours of the information being reported to Princeton Consumer Research.

8.4 Severity

Adverse events are first graded according to seriousness and then severity.

The Investigator will evaluate the severity of each AE. Adverse events will be graded as

Mild: Awareness of symptoms but easily tolerated

Moderate: Discomfort enough to interfere with but not prevent daily activity

Severe: Unable to perform usual activity

8.5 Relationship

The Investigator will judge the likelihood that the AE was related to the study products according to the following criteria

Not related: There is no temporal or causal relationship to the study products.

Related: There is a possible temporal or causal relationship to the study products.

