1.3 Objective

To assess the sensitization potential of OmezaTM Collagen Matrix compared to that of a negative control (0.9% sodium chloride, NaCl) using 9 consecutive continuous applications on the back area over a 3-week induction period, a 10-17-day rest period, and a challenge phase of approximately 48 hours exposure followed by evaluations over 72 (± 2) hours.

The secondary objective is to assess the safety of OmezaTM Collagen Matrix by monitoring adverse events throughout the study.

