2 INVESTIGATIONAL PLAN

2.1 Overall Study Design

This is an evaluator-blinded study using a within-subject randomized design. Each subject will receive all investigational products at the same time. The trained skin evaluator and Investigator will be blinded to the identity of the test materials. The investigational products will be OmezaTM Collagen Matrix liquid and a negative control (0.9% aqueous sodium chloride). The study will involve repetitive and continuous patch applications of all investigational products approximately 48 hours on weekdays and for approximately 72-hour periods over weekends over 3 weeks, for a total of 9 induction applications. Sites on the back area will be evaluated by the blinded trained evaluator after each patch removal. Subjects will have a rest period of 10 – 17 days, followed by challenged applications of each investigational product to naïve sites for approximately 48 hours. Evaluations of the challenge sites will be made approximately 30 minutes, 24 (± 1), 48 (± 2) and 72 (± 2) hours post removal. Total study duration after screening will be approximately 5-6 weeks for each subject.

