8.6 Action Taken and Outcome

The Action Taken with study products for every AE will be reported as either: Dose Not Changed, Dose Interrupted, or Dose Withdrawn. Other actions taken can include none, medication required, or other intervention documented on the AE. The Outcome of each AE will be entered as either: Recovered/Resolved, Recovered/Resolved with Sequelae, Not Recovered/Not Resolved, Fatal, or Unknown.

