13 REPORT

13.1 Final Report

The final report will summarize the method and adverse events relative to the test product and the subjects. A determination of the test product's potential for sensitization, including any necessary discussion, will be included in the report. A demographics table with subject numbers, age, race and gender will be provided as an Appendix in the report.

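### Section 8.5 lets timing alone make an adverse event 'Related', and sections 8.5 and 8.6 take one entry for both products together

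*Combined protocol and SAP*

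**What the plan says.** Section 8.5 leaves causality to the Investigator, under two stated criteria: "The Investigator will judge the likelihood that the AE was related to the study products". The two categories are "Not related: There is no temporal or causal relationship to the study products" and "Related: There is a possible temporal or causal relationship to the study products". There is no middle category and no definition of how close in time an event must be.

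Section 8.6 treats the products in the same collective way: "The Action Taken with study products for every AE will be reported as either" one of three options, which cover dose unchanged, interrupted or withdrawn.

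Section 2.1 sets the exposure: "Each subject will receive all investigational products at the same time", with patches worn continuously for "approximately 48 hours on weekdays and for approximately 72-hour periods over weekends over 3 weeks, for a total of 9 induction applications". A patch-free rest of 10 to 17 days follows, then a challenge patch of about 48 hours and readings up to 72 hours after its removal.

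The safety objective in section 1.3 concerns one product: "The secondary objective is to assess the safety of OmezaTM Collagen Matrix by monitoring adverse events throughout the study". Sections 4.4 and 6.6 allow one product to be stopped on its own. Section 8.1 keeps skin irritation out of the AE record unless it leads to withdrawal.

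**The concern.** The two categories are complements joined by 'or'. A possible temporal relationship is therefore enough for 'Related', and its complete absence is needed for 'Not related'. A subject who catches a cold on Day 10 has both patches on. An Investigator who is sure that the patches did not cause the cold still cannot truthfully record that there is no temporal relationship.

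The second difficulty is the collective wording. A local AE arises at a site, and each site carries one product. The protocol asks for one relationship and one action for the products together and does not require the site to be noted. The within-subject saline control is then not used for AEs.

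At stake is what the AE summary can tell a reader. Incidental events may be counted as related, and a local AE at a Matrix site may not be distinguishable from one at a saline site. No statistical analysis is planned (section 7.2), so the descriptive AE record is the basis for the secondary objective.

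**Working it through.** **Inputs.** Table 5-1 gives the induction visit days 1, 3, 5, 8, 10, 12, 15, 17, 19 and 22, and the challenge days 36, 38, 39, 40 and 41. Section 5.4 gives a rest of 10 to 17 days; the table schedules 14 (Day 22 to Day 36).

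**Step 1: reproduce the plan's duration.** The gaps between induction visits are 2, 2, 3, 2, 2, 3, 2, 2 and 3 days. That is 9 applications and 21 days, as planned. Challenge wear is 38 − 36 = 2 days and follow-up after removal is 41 − 38 = 3 days. Total = 21 + rest + 2 + 3:

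- rest 10: 36 days (5.1 weeks)
- rest 14: 40 days (5.7 weeks)
- rest 17: 43 days (6.1 weeks)

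This agrees with the 5 to 6 weeks stated in section 2.1.

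**Step 2: share of days that meet the temporal limb.** Patch-on days = 21 + 2 = 23. The protocol gives no window after removal, so the windows in the lower rows are assumptions that show the range. A 72-hour window adds 3 days after induction and 3 after challenge (29 days). A 7-day window adds 7 after induction, but only the 3 that remain after challenge (33 days).

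| Meaning given to 'temporal' | Rest 10 (36 d) | Rest 14 (40 d) | Rest 17 (43 d) |
|---|---|---|---|
| Patch on | 23/36 = 63.9% | 23/40 = 57.5% | 23/43 = 53.5% |
| Patch on, or within 72 h (assumed) | 29/36 = 80.6% | 29/40 = 72.5% | 29/43 = 67.4% |
| Patch on, or within 7 days (assumed) | 33/36 = 91.7% | 33/40 = 82.5% | 33/43 = 76.7% |
| Any time after first application (assumed) | 100% | 100% | 100% |

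During induction alone the share is 21/21 = 100% under every row. If incidental AEs fell evenly over time (an assumption), these shares are also the expected proportions classed 'Related' by timing alone.

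**Step 3: can timing separate the products?** Both products go on and come off at the same visits. At any window the temporal limb therefore gives the same answer for Matrix and for saline, unless one has been stopped earlier under section 4.4 or 6.6.

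**Step 4: which AEs does the collective entry affect?** Most patch-site reactions never reach section 8.5, because section 8.1 excludes irritation that does not lead to withdrawal. The local AEs that do reach it are chiefly those that lead to withdrawal. They are few, but they are the ones for which the product matters most. Systemic AEs are outside this point: a subject who wears both products at once gives no basis for splitting a systemic event between them.

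**The case against.** The strongest reply is that this is loose drafting with little consequence, and much of that stands.

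- A reader might infer that nearly every AE becomes 'Related'. The documents do not support that. Patches are on for 54% to 64% of the study, and a share near 100% needs an unlimited window, which section 8.5 permits but does not state.
- A reader might infer that the secondary objective cannot be answered. It is to be met by monitoring AEs, and no related-AE rate is a planned output.
- A reader might infer that true product events are hidden. The rule errs towards over-attribution and drops no AE. Under section 8.3 the sponsor is told of all AEs, and prompt reporting turns on Serious or Unexpected, not on relatedness.
- Skin reactions are already scored and tabulated by site (sections 6.6, 7.2 and 12.2), and section 6.8 compares the test article with the negative control.
- Section 8.1 refers AE recording to the site's standard procedures, which are not in the documents. The AE form may hold a location field. The protocol does not require one.
- Section 13.1 promises a summary of "adverse events relative to the test product" and the subjects, while section 4.1 calls saline a test product too. That sentence alone does not show that the report concerns the Matrix only. The product-specific aim rests on section 1.3.

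Investigator judgement is also offered as a safeguard. It does not remove the problem, because the judgement must follow the two written criteria, and those make timing sufficient. An Investigator could read 'temporal relationship' as more than coincidence in time, but the text gives no such limit.

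**Conclusion.** The rule is wrong as written, with limited consequences. On the literal wording, every AE with onset on Days 1 to 22 or 36 to 38 is 'Related' regardless of the view taken on causation. That is 23 of 40 scheduled days, or 54% to 64% over the permitted rest period, and possibly more because no window is given. The documents give no AE rate, so the number of AEs affected cannot be estimated. Only the share of study time can, and it carries over to AEs only if they fall evenly over time.

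Separately, the relationship and action entries cannot tell Matrix from saline for the local AEs that reach them. It would go too far to say that such AEs are attributed to each product: the text refers to the products as a group and asks for no attribution within it. AE detection, prompt reporting and the site-level skin scores are unaffected, and systemic AEs could not be split by product under any wording.

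**What to change.** In section 8.5, define 'Related' as a reasonable possibility that a study product caused the event, with timing as supporting evidence but not sufficient alone. Define 'Not related' as no reasonable possibility of a causal relationship.

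In sections 8.5 and 8.6, for each local AE, record the site position (and whether it is an original, move or challenge site), and complete relationship and Action Taken for that site. Decode positions to Matrix or saline after scores are final. Tabulate local AEs by product and systemic AEs per subject.

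The blind is kept, because only position is recorded while the study runs. The cost is a few added fields on the AE form, a decoding step and one more table.

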8.6 Action Taken and Outcome

The Action Taken with study products for every AE will be reported as either: Dose Not Changed, Dose Interrupted, or Dose Withdrawn. Other actions taken can include none, medication required, or other intervention documented on the AE. The Outcome of each AE will be entered as either: Recovered/Resolved, Recovered/Resolved with Sequelae, Not Recovered/Not Resolved, Fatal, or Unknown.

9 INVESTIGATOR OBLIGATIONS

9.1 Ethical and Regulatory Considerations

This study will be conducted in accordance with GCP, Title 21 of the Code of Federal Regulations (CFR), Part 50, Subparts A and B; Part 56, and the Standard Operating Procedures (SOPs) of Princeton Consumer Research and the study protocol and protocol amendment(s) if any.

